### **Primary endpoint**

1. Compare the rate of adequate specimens obtained by slow pull vs dry suction vs wet suction techniques using the new fine needle biopsy (FNB) needles in solid lesions.

### **Secondary outcome**

1. Compare the degree of blood contamination obtained by all three techniques.

### **Inclusion criteria**

- b. Ages 18 years and older
- c. Male or female
- d. Patients who require EUS and tissue sampling of solid lesions (size >1 cm) anywhere in the body: lymph nodes, stomach, esophagus, colon, small intestine, pancreas, liver, spleen or kidney.
- e. Patients who are able to give consent

### **Exclusion criteria**

- a) Pregnant female
- b) Coagulation disorders (platelets < 50,000/mm^3, INR > 2)
- c) Patients with acute pancreatitis in the immediate 2 weeks prior to the procedure (if the lesion to be biopsied is in the pancreas).
- d) Cardiorespiratory dysfunction that precludes sedation.
- e) Unable to provide informed consent
- f) Previous chemotherapy or radiotherapy for pancreatic neoplasm

**Patient Enrollment:** Patients will be prospectively enrolled until the target sample size has been reached. This study is planned as a single-blind, parallel group randomized trial. There will be three parallel groups. The first group will be assigned to the slow pull technique, the second one to the dry suction technique and the third one to the wet suction technique. Our calculated sample size is 300 patients. In our unit, we perform approximately 10 – 15 EUS guided pancreatic mass biopsies per month. Therefore, we expect to enroll the desired number of patients in approximately 60 months.

### **Data Collection:**

For each patient, the following data will be collected:

1. Age
2. Gender
3. Ethnicity
4. EUS characteristics of the lesion (number, location, size, echogenic pattern, invasion into other structures)
5. Number of needle passes
6. Other maneuvers if 3 passes yields an inadequate specimen
7. Immediate complications (bleeding, perforation, hemodynamic instability)

### **Statistical analysis**

Sample size: The sample size computation was done on the basis of published data . A previous study [11] showed that Wet suction technique produced moderate to high cellularity (67.5%) compared to conventional FNA technique (44.4%). Another manuscript demonstrated that slow-pull technique had higher moderate to high cellularity (71%) as compared to suction technique with 5-mL (57.9%) . Other studies  reported cellularity between 46% and 73.6%. Based on this prior information, we assumed that one of the techniques will yield at least 25% higher cellularity compared to the baseline 45%. Based on this, a sample size of 95 per group will be sufficient to detect significant difference in at least one pair of techniques with more than 80% power and at 1% level of significance using a two-sided Z-test with pooled variance. Further, we also validated sample size computation for comparing average cellularity score across three groups. A study reported average cellularity score by dry technique as 1.85 (SD: 0.79) and by WET as 1.70 (SD:0.72) compared to average 1.45 (SD: 0.78) . Using this information, a sample size of 100 per group will be sufficient to detect significant difference in average cellularity scores among groups using a one way analysis of variance (F-test) with 80% power and at 1% level of significance. The level of significance was adjusted due to multiple comparisons in both calculations. This sample size seems to be appropriate for detecting significant differences in other outcomes (such as diagnostic yield) as well. The sample size computation was carried out using PASS 14 (PASS 14 Power Analysis and Sample Size Software (2015). NCSS, LLC. Kaysville, Utah, USA, [ncss.com/software/pass](http://ncss.com/software/pass).)

Statistical Analysis: All categorical variables will be described using count and percentage whereas the quantitative variables will be described using mean and standard deviation(SD). The baseline characteristics will be compared among three groups using either one way analysis of variance (for quantitative data) or Fisher's exact tests (for categorical data). The primary outcome (cellularity score: quantitative and categorical forms and percentage positive diagnostic yield) will be compared between groups using an F-test or Fisher's exact tests. The proportion differences between two groups will be compared using two sided Z-test between two groups

while quantitative scores will be compared using t-tests with Bonferroni corrected method. The effect size will be summarized using proportion difference along with 95% confidence interval (CI) estimated using Binomial distribution. Further, relative risk regression analysis will be performed for determining adjusted differences in cellularity and diagnostic yields between groups. The regression analysis will be carried out separately for each outcome. This analysis will also help to identify any factors associated with increased percentage of cellularity and diagnostic yield. The secondary outcomes will also be compared between groups using a Fisher's exact test or an F-test depending on the type of outcome. The results of relative risk regression analysis will be summarized using relative risk along with 95%CI and p-value. P-values less than 5% will be considered statistically significant results. All the statistical analyses will be processed using STATA 14 and SAS 9.4.

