### **OBJECTIVES**

The primary objective of this study is to compare the rate of adequacy for cytologic and/or histologic diagnosis of specimens obtained using three different techniques of tissue acquisition when performing EUS guided sampling of solid lesions with FNB needles. The three techniques to be compared are: SP, DS and WS. The secondary objectives are to compare the rate of blood contamination of the specimen obtained by each technique

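### The primary outcome and the significance level differ between sections, and the stated power is shown for cellularity but not for the adequacy rate

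*Combined protocol and SAP*

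**What the plan says.** **Outcome.** The Objectives section sets out to "compare the rate of adequacy for cytologic and/or histologic diagnosis of specimens", and the Primary endpoint section agrees: "Compare the rate of adequate specimens obtained by slow pull vs dry suction vs wet suction techniques". The analysis paragraph of the Statistical analysis section reads differently: "The primary outcome (cellularity score: quantitative and categorical forms and percentage positive diagnostic yield"), to be compared by an F-test or Fisher's exact tests. The sample size paragraph of that section works with the proportion of moderate-to-high cellularity and adds a check on the mean cellularity score. Its main assumption is "we assumed that one of the techniques will yield at least 25% higher cellularity compared to the baseline 45" per cent.

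**Adequacy.** Methods defines it by the score: 2 or more for cytological diagnosis and 4 or more for histological diagnosis. The Appendix gives the 0–5 scale, on which 3 means limited histological material.

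**Significance level.** The sample size paragraph uses 1% and explains: "The level of significance was adjusted due to multiple comparisons in both calculations". For proportions, the analysis paragraph says "The proportion differences between two groups will be compared using two sided Z-test between two groups". Only the clause after that one, on the scores, names a correction: "while quantitative scores will be compared using t-tests with Bonferroni corrected method". The threshold comes near the end of the paragraph: "P-values less than 5% will be considered statistically significant results".

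**Size.** The Z-test calculation gives 95 per group for a difference in at least one pair of techniques, with power above 80%. The one-way ANOVA check gives 100 per group. Patient Enrollment gives 300 in total.

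**The concern.** Three parts of the plan should describe one test of one outcome: the endpoint, the sample size and the analysis. Here they describe different outcomes, and two of them give different levels.

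Followed literally, the analysis paragraph offers three primary analyses: mean score, categorised score and diagnostic yield. It does not name the adequacy rate, which the endpoint section makes primary. The threshold for a pairwise difference in proportions could be 5%, 1.67% or 1%, depending on which sentence governs. If these choices stay open until the data are seen, a claim that one technique is better could rest on the most favourable combination. A reader also cannot tell which outcome, cut-off and level the 80% power refers to.

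**Working it through.** **1. The plan's own figure.** Inputs from the sample size paragraph: p1 = 0.45, p2 = 0.70 (25 read as percentage points), two-sided level 1%, pooled Z-test, 95 per group. Power for one pair is

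Φ{ [ |p2 − p1|·√n − z·√(2p̄(1 − p̄)) ] / √(p1(1 − p1) + p2(1 − p2)) }, with p̄ = 0.575 and z = 2.576.

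- Pooled term: √(2 × 0.575 × 0.425) = 0.6991.
- Unpooled term: √(0.2475 + 0.2100) = 0.6764.
- n = 95: (0.25 × 9.747 − 2.576 × 0.6991)/0.6764 = 0.94, so power is **82.6%**.
- n = 100: (2.500 − 1.801)/0.6764 = 1.03, so power is **84.9%**.

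This agrees with the plan. Reading the 25% as relative (45% vs 56.25%) gives 15.1% at 95 per group, so the absolute reading is the intended one. For at least one of three pairs, with true rates 45/45/70%, simulation gives about 93–94% at 95–100 per group.

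The ANOVA check also holds. The means 1.85, 1.70 and 1.45 have squared deviations summing to 0.0817, and the pooled SD is 0.764. The noncentrality at 100 per group is 100 × 0.0817/0.764² = 14.0, which gives 79.6% at 1% against the stated 80%.

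**2. Does that power carry over to adequacy?** Background reports both measures for the same earlier study of wet suction: cellularity 68% vs 44% and adequacy 85% vs 75%. The contrasts are 24 and 10 points, so power for one is not power for the other. No section gives an assumed adequacy rate for this trial. The same formula gives the rate detectable with 80% power for one pair at 100 per group:

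| Level | Baseline 45% | Baseline 75% |
|---|---|---|
| 1% | 68.8% | 92.7% |
| 1.67% | 67.5% | 91.9% |

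**3. What the level changes.** Chance of at least one false positive among three pairwise pooled Z-tests when all techniques share one true rate (45% to 75%), 95–100 per group:

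| Rule for the Z-tests | Familywise error |
|---|---|
| 5% each, no gate | 11.8–13.3% |
| 5% each, only after a significant overall Fisher test | 4.8–4.9% |
| Bonferroni, 0.05/3 = 1.67% each | 4.2–4.9% |
| 1% each | 2.5–2.8% |

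The first three rows are exact enumerations and the last is simulated.

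**The case against.** **The outcomes may be one construct.** Adequacy is a cut-off on the cellularity score, and Background states the aim in terms of cellularity. The categorical form of the score may therefore mean adequacy. That is plausible, but no section says so. It also leaves mean score and diagnostic yield as further primary outcomes, and yield is not defined as a cut-off on the score.

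**The two cut-offs need not conflict.** Read naturally, a score of 3 is adequate for cytology and not for histology. This stands: there is no contradiction. A single adequacy rate still needs one stated cut-off.

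**The intent to adjust is documented.** The sample size paragraph says that both calculations were adjusted. The Bonferroni phrase could be stretched to cover the Z-tests, and the overall test is listed before the pairwise ones. On either of those readings the familywise error is below 5%. This also stands, so 12–13% is what one reading permits and not what the plan prescribes. Even so, Bonferroni for three pairs gives 1.67%, which is not the 1% used in design.

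**A reader might infer that the plan's cited cellularity differences give under 80% power.** For one pre-chosen pair at 1%, 44.4% vs 67.5% gives 74.2% at 95 and 76.9% at 100 per group. But the plan claims power for at least one pair. Simulated that way, the 23.1-point difference gives 88–90% when the third arm sits at either end, and 77–78% only when it lies midway. The 13.1-point difference (57.9% vs 71%) does stay low, at 37–40% with two arms at the lower rate. The 25 points remain a planning assumption that the sponsor may make.

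**Conclusion.** The conflict is real and should be fixed. The primary outcome differs between the endpoint sections, the sample size paragraph and the analysis paragraph. The level is 1% in design and 5% in analysis, with no stated correction or gate for the Z-tests on proportions. At stake is a familywise error anywhere from about 2.5% to about 13%, depending on the reading, assuming equal true rates of 45–75% and 95–100 per group.

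The sample size arithmetic is correct for cellularity of 45% vs 70%. A reader might infer that the trial is underpowered for adequacy; the documents do not support that. Background's 75% vs 85% adequacy would give about 20% power for one pair at 1%, but its contrast of 37.5% vs 76.7% for a score of 2 or more would give above 99%. Both come from aspiration-needle studies and neither is a planning assumption here. What can be said is that power for the named endpoint is not shown. Nor is the ANOVA stated to be the basis for 100 per group: the plan calls it a validation.

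**What to change.** Keep 300 patients and reword.

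- **Outcome.** In the analysis paragraph, name the adequacy rate of the Objectives and Primary endpoint sections as the single primary outcome. State which Methods cut-off defines it, so that a score of 3 is classified. Make mean score and diagnostic yield secondary.
- **Level.** Use one level and one multiplicity rule for the pairwise Z-tests in both paragraphs. Either carry the 1% design level into the analysis, or use Bonferroni at 0.05/3 = 1.67% in both. Say whether the pairwise tests depend on a significant overall test.
- **Power.** State that the 80% refers to cellularity of 45% vs 70%. Add the adequacy difference detectable with 80% power for one pair at 100 per group, for the chosen level only: at 1%, 45% vs 68.8% and 75% vs 92.7%; at 1.67%, 45% vs 67.5% and 75% vs 91.9%. Say which baseline is the planning assumption.

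The cost is rewording and no extra patients. The choice among several primary outcomes is given up. A stricter pairwise threshold lowers power: for one pair at 45% vs 70% and 100 per group, 84.9% at 1% or 88.9% at 1.67%, against 95.3% at 5%. If baseline adequacy is high, the printed detectable rate will lie close to the ceiling.

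### The pairwise proportion tests are sized at a multiplicity-adjusted 1% but judged at 5% with no clear correction or gate, and the analysis text lists more primary outcomes than the protocol names

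*Combined protocol and SAP*

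**What the plan says.** All places are in the combined protocol and SAP.

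- **Statistical analysis, sample-size paragraph.** The proportion calculation gives 95 per group "at 1% level of significance using a two-sided Z-test with pooled variance". The score calculation finds that "a sample size of 100 per group will be sufficient to detect significant difference in average cellularity scores among groups", by an F-test also at 1%. The reason for the level follows: "The level of significance was adjusted due to multiple comparisons in both calculations". The divisor is not given. Diagnostic yield appears only in a closing remark: "This sample size seems to be appropriate for detecting significant differences in other outcomes (such as diagnostic yield) as well".
- **Statistical analysis, analysis paragraph.** "The primary outcome (cellularity score: quantitative and categorical forms and percentage positive diagnostic yield) will be compared between groups", by F-test or Fisher's exact test. The pairwise tests follow in a single sentence of two clauses. The first deals with proportions: "The proportion differences between two groups will be compared using two sided Z-test between two groups". The second deals with the scores, and it is here that a correction is named: "while quantitative scores will be compared using t-tests with Bonferroni corrected method". Proportion differences get 95% intervals, and a relative-risk regression is planned for each outcome. The closing rule is "P-values less than 5% will be considered statistically significant results". The 1% level is not mentioned again.
- **Objectives and Primary endpoint.** Only the rate of adequate specimens is named.
- **Methods and Appendix.** A score of 2 or more is adequate for cytology and 4 or more for histology, on one scale from 0 to 5.

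**The concern.** An adjustment made when sizing a trial protects against false positives only if the analysis applies it. Here the analysis text does not clearly do so for the comparison that was sized. A pairwise adequacy p-value of 0.03 would be positive under the 5% rule, and negative at 0.05/3 or at the 1% used for sizing.

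The second gap adds to the first. With three variables called primary and no ranking, a favourable mean score or diagnostic yield could be reported as success on the primary outcome when adequacy shows nothing. The plan does not fix in advance which result makes the trial positive, so that choice could be made after the data are seen.

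**Working it through.** **1. The plan's own sizings.** Inputs from the sample-size paragraph: 45% versus 70% (the 25% read as absolute), two-sided 1%, pooled Z-test, 95 per group.

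Power = Φ[(Δ√n − z·√(2p̄(1−p̄))) / √(p₁(1−p₁)+p₂(1−p₂))]

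Here Δ = 0.25 and p̄ = 0.575, so √(2 × 0.575 × 0.425) = 0.699 and √(0.2475 + 0.21) = 0.676. With n = 95 and z = 2.576: (2.437 − 1.801)/0.676 = 0.94, which gives **82.6%**. This agrees with the stated figure of more than 80%.

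F-test: means 1.85, 1.70 and 1.45 have squared deviations summing to 0.0817. The mean of the squared SDs (0.79, 0.72, 0.78) is 0.584. Noncentrality at 100 per group is 100 × 0.0817/0.584 = 14.0, and power at 1% is **79.6%**, in line with the stated 80%. At 95 per group it is 76.9%, so the F-test is what sets 100 per group.

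**2. False pairwise results on one proportion outcome.** Three equal arms, 100 per group, no true difference. The second column is normal theory. The third is binomial simulation at common rates from 45% to 90%, with pooled Z-tests and a three-group Fisher test.

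| Reading | Normal theory | Binomial |
|---|---|---|
| Z-tests at 5%, no gate (literal) | 12.2% | 12.1–13.2% |
| Z-tests at 0.05/3 (Bonferroni covers them) | 4.4% | 4.2–5.0% |
| Z-tests at 1% (as sized) | 2.7% | 2.5–2.8% |
| Z-tests at 5% only after a significant 5% overall test | 5.0% | 4.6–4.9% |

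**3. Across the listed primary variables.** The total error is at least the largest single-variable error and at most their sum. Mean-score t-tests carry Bonferroni on every reading (4.4%). The upper limits for mean score, categorical score and yield are therefore:

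- literal: 4.4 + 12.2 + 12.2 = 28.8%
- Bonferroni throughout: 4.4 + 4.4 + 4.4 = 13.2%
- gated: 4.4 + 5.0 + 5.0 = 14.4%

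Placing the error within these limits needs inputs that the documents do not give. The assumptions were adequacy 45, 75 or 90%; a score cut-off of 2 or 4; yield 45, 75 or 90%; and a latent score–yield correlation of 0.3, 0.6, 0.9 or 0.99. That makes 3 × 2 × 3 × 4 = 72 settings. The results were 17.1–26.3% (literal), 8.1–12.1% (Bonferroni, pairwise tests only) and 8.4–12.4% (gated). Spreading the score levels evenly gives nearly the same: 16.8–25.9% literal and 8.0–12.2% with Bonferroni.

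**4. Power once a rule is fixed.** Same formula, 45% versus 70%, n = 100:

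- 5%: (2.5 − 1.370)/0.676 = 1.67, power **95.3%**
- 0.05/3: (2.5 − 1.674)/0.676 = 1.22, power **88.9%**
- 1%: (2.5 − 1.801)/0.676 = 1.03, power **84.9%**
- pairs at 5% after a significant overall Fisher test: 90.5–94.5% by simulation, depending on the third arm

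**The case against.** The strongest reply is that the authors probably did mean to correct the Z-tests. The Z-test and t-test clauses are one sentence that ends with Bonferroni, and the sample-size paragraph says both calculations were adjusted. A Bonferroni-adjusted p-value is properly compared with 5%, so the 5% rule does not by itself contradict sizing at a stricter per-test level. The overall test is also listed before the pairwise tests, which suits an overall-then-pairs procedure. On either milder reading, error for one outcome is about 5% or less.

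This stands in part. A reader might infer that the plan leaves the Z-tests uncorrected and that a 12% error rate is its settled consequence. The text does not support that: 12–13% belongs to one of three readings. But neither milder rule is written down, and neither deals with several primary variables.

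Two other strong inferences also fail. One is that the trial is wrongly sized: both calculations reproduce, and 1% is stricter than Bonferroni for three pairs requires. The other is that adequacy has no usable cut-off. The Objectives allow cytologic and/or histologic adequacy, and on a single 0–5 scale any score of 4 or more is also 2 or more, so the definition reduces to 2 or more. It needs confirming only.

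The remark on other outcomes is weak evidence that yield was meant as secondary, since it may only mean outcomes not used in the sizing. The mismatch with the Objectives and Primary endpoint sections does not depend on it.

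**Conclusion.** The point holds as a defect in the decision rule. It should be fixed before analysis. The error for one proportion outcome is about 12–13% read literally, 4–5% with Bonferroni, and 5% with a gate. These figures need only three equal arms of 100 and no true difference, and they change little with the common rate.

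The conclusion that error across the listed primary variables can exceed 5% applies on every reading. Its size, roughly 8–12% on the milder readings and 17–26% on the literal one, is illustrative because rates, score distribution and correlations are assumed.

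**What to change.** In the analysis paragraph:

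1. Name the proportion of adequate specimens as the single primary outcome, matching the Objectives and Primary endpoint, and confirm its cut-off.
2. Make mean cellularity and diagnostic yield secondary. Keep the Bonferroni correction already stated for the mean-score t-tests.
3. State one rule for the three primary Z-tests. **Either** judge each at 0.05/3, or at the 1% used for sizing, with matching 98.3% or 99% intervals, and say that the overall test is not a separate route to significance. **Or** test pairs at 5% only after a three-group Fisher test significant at 5%. With three arms this gate is enough: if any arm differs, at most one pair can still be truly equal.
4. Describe the relative-risk regression as supportive.

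No patients are added. The costs are that mean cellularity, whose F-test set 100 per group, becomes secondary, and that some pairwise results with p below 5% no longer count. Power at the planned effect stays at 84.9% or more. Correcting all nine pairwise tests (three pairs, three variables) at 0.05/9 instead would give 79.7%, just under target.

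The relative loss is larger for smaller differences. At 75% versus 85% adequacy (one FNA study in the Background, illustrative), power is already only 42.3% at 5%. It would fall to 26.4% at 0.05/3 or 20.8% at 1%. The fix worsens that low power but does not create it.

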## **METHODS**

Patients will be enrolled in a prospective manner at the University Medical Center of El Paso endoscopy unit. At the time of the pre-op appointment the nurse will perform the usual evaluation of the patient and will explain the EUS/FNB procedure. The day of the procedure, the endoscopist performing the procedure explain the EUS/FNB procedure and the risks of the procedure, explain the study and will consent the patients. He will randomize them using a random number list generated by a simple block randomization scheme by our study statistician, to one of three possible groups: SP, DS or WS. The randomization number will be kept in sealed opaque envelopes in numerical sequence. The random number sequence will be generated using SAS software. The patients will be asked to sign the consent only after the study has been explained to them and all their questions have been answered by the performing physician. The randomization will be via sealed envelopes that will contain cards with the technique and the needle to be used. Following randomization each patient will be assigned a code corresponding to one of the three technique arms. This code will be noted and placed in a master spreadsheet that only the study coordinator and/or assigned research personnel will handle.

All the procedures will be performed by three experienced endoscopists ([name]., [name]. and [name].) using 22 gauge SharkCore™ (MEDTRONIC) or Acquire™ (BOSTON SCIENTIFIC) FNB needles. The techniques to be used are described here:

DS: the stylet will be left in place in the needle and once the lesion has been punctured, the stylet will be withdrawn. After this, negative pressure with a 10 cc syringe will be applied to the needle. Once the lesion has been punctured, the valve between the syringe and the needle will be opened and the endoscopist will obtain the sample with multiple back and forth movements.

SP: the stylet will be left inside the needle and retracted slightly prior to puncturing the lesion in order to sharpen the needle. Once the lesion has been punctured, the stylet will be pushed completely into the needle to expel any debris from the gastrointestinal wall, then it will be

5/7/2020

slowly withdrawn from the needle as the endoscopist is making the back and forth movements to create negative pressure in the system.

WS: Prior to puncturing the needle, the stylet will be completely withdrawn and the needle will be flushed with 10 cc of normal saline until the entire needle lumen is completely primed with fluid. After this, negative pressure with a 10 cc syringe containing 1 cc of NS will be applied in a similar manner as in the DS technique. The procedures will be performed under deep sedation according to the principles of monitored anesthesia care. The patients will be anesthetized with intravenous administration of propofol by trained anesthesiologists. Once the lesion is evaluated by EUS, the endoscopist will select the shortest pathway, while avoiding blood vessels, to reach the pancreatic lesion. Under real-time visualization, each lesion will be punctured with 3 needle passes.

If the tissue sample is deemed suboptimal after these 3 passes, then the endoscopist will be allowed to use a different needle and/or technique according to his preference. The specimen obtained will be assessed preliminarily by the cytology technician who will determine if more tissue is needed. Once the tissue is deemed to be sufficient, the pathologist evaluating the specimen will dictate the official cellularity and blood contamination scores according to scales previously described by Gerke et al  and Wee et al . These will be the scores used for analysis. A score of  $\geq 2$  and  $\geq 4$  will be considered adequate for cytological and histological diagnosis respectively. The pathologists evaluating the sample will be blinded to the type of needle and technique used.

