## **RESEARCH PLAN**

### **Study Design**

This study is planned as a single-blind, parallel group randomized clinical trial (RCT). After receiving consent from the eligible subjects, the subjects will be randomly assigned to one of the three techniques and one of two needles, stratified by the three (3) endoscopists performing EUS-FNB.

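### The analysed cellularity and blood scores are not limited to tissue obtained with the randomised technique, so a failed technique can be credited with a rescue success

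*Combined protocol and SAP*

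**What the plan says.** The Primary endpoint section sets the aim: "Compare the rate of adequate specimens obtained by slow pull vs dry suction vs wet suction techniques". Under Study Design, "the subjects will be randomly assigned to one of the three techniques and one of two needles", so both technique and needle are part of the allocation.

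METHODS then gives the order of events for the specimen:

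1. Three passes are made.
2. If the sample is judged suboptimal after these, "the endoscopist will be allowed to use a different needle and/or technique according to his preference".
3. The specimen is "assessed preliminarily by the cytology technician who will determine if more tissue is needed".
4. "Once the tissue is deemed to be sufficient, the pathologist evaluating the specimen will dictate the official cellularity and blood contamination scores", on two published scales.
5. "These will be the scores used for analysis".

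Adequacy is a score of at least 2 (cytology) or at least 4 (histology), and the pathologist is blinded to needle and technique. Data Collection includes the item "Other maneuvers if 3 passes yields an inadequate specimen". The Statistical Analysis text compares groups by F-test or Fisher's exact test and makes no use of that item.

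**The concern.** The endpoint is meant to describe what each technique yields, but the only operational scoring rule places the score after any rescue. A patient allocated to slow pull whose three passes fail, and who then has a good sample taken by wet suction, can be recorded as an adequate slow-pull specimen.

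Scoring is also tied to tissue having been judged sufficient. The plan does not say what score a patient receives if that point is never reached, although the Appendix scale has a 0 for insufficient material. This conditioning on success is only partial, because the gate is the technician's preliminary judgement while the endpoint is the pathologist's score.

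Blinding the pathologist does not help, since the problem is which tissue is being scored. At stake is whether the trial can detect a real difference between techniques and attribute it correctly, for both the primary endpoint and the blood contamination outcome.

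**Working it through.** **Inputs.** From the sample-size text under Statistical analysis: baseline 45%; one technique 25% higher, read as 25 points, so 70%; two-sided pooled-variance Z-test; 1% level; 95 per group, and 100 per group from the second calculation. From Patient Enrollment: 300 patients in total. From the Statistical Analysis text: p-values below 5% are called significant.

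**The plan's own figure.** With rates p₁ and p₂, mean rate p̄ and n per group:

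- SE₀ = √[2p̄(1 − p̄)/n]
- SE₁ = √[(p₁(1 − p₁) + p₂(1 − p₂))/n]
- power = Φ[(d − z·SE₀)/SE₁] + Φ[(−d − z·SE₀)/SE₁], where d = p₂ − p₁ (the second term is negligible except when d is small)

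For 0.45 vs 0.70, n = 95 and z = 2.576, SE₀ = 0.0717 and SE₁ = 0.0694. Then (0.25 − 0.1848)/0.0694 = 0.94, so power is 82.6%. This agrees with the plan's claim to "detect significant difference in at least one pair of techniques with more than 80% power and at 1% level of significance". At n = 100 it is 84.9%. The 25-point reading is the one that fits: a relative 25% (45% vs 56.25%) would need 460 per group.

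**Adding rescue.** Let r be the share of all three-pass failures that are scored adequate after further passes. The documents give no value, so r is an assumption. The analysed rate in an arm is

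p′ = p + (1 − p)r.

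With the same r in both arms, the difference is (p₂ − p₁)(1 − r) = 25(1 − r) points. At n = 100 per group:

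| r | Analysed rates | Difference (points) | Power, 1% level | Power, 5% level |
|---|---|---|---|---|
| 0 | 45.0% vs 70.0% | 25.0 | 84.9% | 95.3% |
| 0.10 | 50.5% vs 73.0% | 22.5 | 76.3% | 91.2% |
| 0.25 | 58.75% vs 77.5% | 18.75 | 60.8% | 81.7% |
| 0.50 | 72.5% vs 85.0% | 12.5 | 33.7% | 58.0% |
| 0.80 | 89.0% vs 94.0% | 5.0 | 9.5% | 24.4% |

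Power reaches 80% at r = 0.060 (1% level) and r = 0.272 (5% level), and is lower for any larger r.

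**Unequal rescue.** With r_w in the worse arm and r_b in the better arm:

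difference = 0.25 + 0.30·r_b − 0.55·r_w.

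- It widens when r_b > (0.55/0.30)·r_w = 1.83·r_w. Example: r_w = 0.25, r_b = 0.50 gives 85.0 − 58.75 = 26.25 points.
- It reverses when r_w > (0.25 + 0.30·r_b)/0.55 = 0.455 + 0.545·r_b. Example: r_w = 0.50, r_b = 0 gives 70.0 − 72.5 = −2.5 points.

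Shrinkage is the expected direction, but it is not guaranteed.

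**The case against.** **Pooling is inferred.** METHODS never says outright that rescue tissue is merged into the scored specimen. The objectives and endpoint speak of specimens obtained with each technique, the data item on further maneuvers treats inadequacy as a result of the three passes, and the scale keeps scores of 0, 1 and 3. This shows what was probably intended, but none of it is a scoring rule. The one rule there is permits post-rescue tissue to be scored, and nothing excludes it.

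**Not every rescue is a change of technique.** Extra passes with the assigned technique, or a swap of needle only, do not credit another technique. That is right, and r above does not separate them. But the needle is also randomised, and extra passes make patients within an arm non-comparable, so these cases too need a rule.

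**Large r is unlikely.** Only samples flagged at the bedside reach rescue, so failures that the technician passes stay failures. Because r is the net share of all three-pass failures, this limit is already inside it; it does make values such as 0.80 less plausible. The 6% crossing also belongs to the 1% planning level, and at 5% the crossing is about 27%.

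**Separate containers may show the pathologist that rescue took place.** This is a fair practical point. The technique and needle stay masked, and coded labels would reduce the problem.

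**This is simply intention-to-treat.** Intention-to-treat keeps patients in their randomised arm; it does not decide which tissue is scored. A post-rescue score measures the assigned technique plus free-choice rescue, which is a different question from the stated one.

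**Conclusion.** The concern holds. As written, the scoring rule allows the primary and secondary scores to rest on tissue from a needle or technique the patient was not allocated to, and it leaves never-sufficient specimens without a defined value. That much follows from the text and is certain.

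The size is not certain. It depends on a rescue share the documents do not give, on the plan's 45% vs 70% cellularity assumption, and on a binary adequacy rate; the full 0–5 score and the cut-off of 4 might still separate the arms. On those terms, modest equal rescue is enough to take the trial below 80% power at its own planning level, and unequal rescue can bias the comparison in either direction. More patients would not cure misattribution, and tissue pooled without labels cannot be separated later. The rule should therefore be settled in the protocol and not left to the analysis stage.

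**What to change.** In METHODS and the statistical section, state the following:

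- The primary cellularity/adequacy score and the blood contamination score are the blinded pathologist's scores on material from the first three passes with the randomised technique and needle, labelled and submitted separately from anything obtained later.
- That material is scored whether or not it is deemed sufficient.
- Every biopsied patient is analysed in the randomised arm. Because the Abstract allows a lesion to go without biopsy after EUS, also report by arm how many randomised patients were not biopsied.
- Adequacy after rescue is reported as a separate outcome, and the plan says which material the diagnostic yield rests on.
- Counting any recorded rescue (Data Collection item 6) as inadequate is a sensitivity analysis only, or a last resort where material cannot be separated. The endoscopist knows the allocation and the technician's blinding is not stated, so the decision to rescue may itself depend on the arm.

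The cost is wording, separate labelling, and a second score for rescued patients only. Observed adequacy rates will be lower than under post-rescue scoring. The planned contrast stays at 45% vs 70%, so the sample size need not change on this account, and the clinical rescue rule is left as it is.
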